This document is the statistical analysis plan (SAP) for a randomized (1:1), non inferiority, clinical trial about initial high-dose oral antibiotics treatment (OT) versus initial intravenous antibiotics treatment (IVT) among children with bone and joint infection (BJI). The primary outcome is the presence of sequelae at 6 months. The protocol of this study was previously published, by Nielsen et al. [11]. There are no major changes to the protocol-planned analyses, but a few minor changes exist. These are summarized in Section 6.5.

3.1 Objectives, Endpoints, and Estimands

3.1.1 Primary

The primary objective is to show that initial high-dose Oral Treatment (OT) is not inferior to initial IntraVenous Treatment (IVT) with respect to the risk of sequelae after 6 months. A non inferiority margin of 5% difference in risk was pre-specified. Accordingly, the primary outcome is the presence of abnormal mobility or function of the affected joint/bone at 6 months follow-up, as evaluated by a blinded clinical examination by a qualified clinician.

Specifically, the two interventions being investigated are initiating either OT or IVT and continuing the treatment until the first of these two events occurs:

- clinical improvement (pain and mobility) and paraclinical improvement (decreasing C-reactive protein) or 3 days (whichever comes last)
- OT or IVT is no longer compatible with good clinical care (e.g. insufficient clinical effect of either OT or IVT, the patient/child is not accepting or tolerating OT or IVT.)

After this initial treatment duration, a follow-up treatment using OT with reduced dose is planned for 1 week in case of joint infection only, 4 weeks in case of spondylodiscitis and 3 weeks in case of other bone infections.

The primary clinical question of interest is: *“Is the risk of having sequelae 6 months after BJI not more than 5% higher when initiating high dose OT as compared to IVT, regardless of initiation of any additional interventions during the follow-up, including switching treatment (from OT to IVT or the other way around), when needed to ensure good clinical care?”*

Accordingly, the primary estimand is described by the following attributes:

- Population: Children and adolescents (3 months to 18 years) with suspicion of first uncomplicated BJI, possibly already treated with either OT or IVT for up to 24h and for whom the suspicion of BJI will not be abandoned within 6 months.
- Endpoint: Presence of an abnormal mobility or function of the affected joint/bone at 6 months follow-up, as evaluated by a blinded clinical examination by a qualified pediatrician and/or pediatric orthopedic surgeon.
- Treatment: The investigational interventions (initiating high-dose OT vs IVT) regardless of any subsequent treatment decision needed to ensure good clinical care (“treatment policy strategy”, see [7]).
- The intercurrent event “any subsequent treatment decision” is addressed by the treatment condition of interest attribute (“treatment policy strategy”, see [7]). The intercurrent event “suspicion of infection is abandoned” is addressed by the population of interest attribute (“Principal stratum strategy”, see [7])
- Population-level summary: Difference in 6-month risk of sequelae between treatment conditions

Remark: the rationale for the above “population” and “intercurrent events” attributes, is the following. The population (defined above) slightly differs from that of the research question (“children with BJI” versus “children with suspicion of BJI, for whom the suspicion of BJI will not be abandoned within 6 months”). This is because it was impossible to include children for which BJI was present with perfect certainty (due to necessity of acute inclusion) and because the population definition of the estimand was chosen to match the inclusion/exclusion criteria. However, we could not think of any reason why the population of the estimand should differ from that of the research question by more than a negligible proportion of patients, equally distributed between the two treatment arms. Hence, we think that for all practical purposes, the two populations can be considered as the same.

3.1.2 Secondary

There are two secondary outcomes:

1. Treatment failure within 28 days. It is defined by two pediatric specialists as a change of antibiotic therapy due to non-acute treatment failure. Although the two specialists are not restricted to define treatment failure, it was suggested in the protocol to define it following these parameters:
 - Temperature above 38.5°C after more than 72 hours of antibiotic therapy.
 - Increasing C-reactive protein after more than 96 hours of antibiotic therapy.
 - No improvement in mobility or pain after 120 hours of antibiotic therapy.
2. Recurrent infection within 6 months. It is defined as the occurrence of (at least one) recurrence of symptoms and signs (same anatomical location) after completion of antibiotic treatment requiring further antibiotic administration.

Correspondingly, the secondary objectives are to estimate the risks for each of the two secondary outcomes, with OT and IVT; as well as the risk differences. The clinical questions of interest are:

“What are the risks of treatment failure within 28 days when initiating high-dose OT and IVT, regardless of any additional interventions, when needed to ensure good clinical care? What is the corresponding risk difference?”

“What are the risks of recurrent infection within 6 months when initiating high-dose OT and IVT, regardless of initiation of any additional interventions during the follow-up, including switching treatment (from OT to IVT or the other way around), when needed to ensure good clinical care? What is the corresponding risk difference?”

Accordingly, the corresponding estimands are defined as the primary estimand of Sec. 3.1.1, except for the endpoint attributes, which are defined by the above items 1 and 2.

3.2 Study Design

This is a two-arm, randomized (1:1), parallel, nationwide open-label non-inferiority clinical trial. Only the assessment of the primary outcome is blinded. Randomization was stratified by C-reactive protein (< 35 vs ≥ 35 mg/L). Patients are followed up until the 12-month follow-up visit (which can take place between 11 and 14 months after randomization), although the primary outcome is defined at the 6-month follow-up visit (which can take place between 5 and 9 months after randomization). Outcomes are defined by the medical examinations at the two planned visits (6 or 12 months), clinical examinations during the course of the disease and via self-reported (electronic) questionnaires, filled in by the patients or their parents. The questionnaires provide daily and weekly patient reported outcomes.

4 Statistical Hypotheses

The null hypothesis to be tested in relation to the primary estimand (detailed in Sec. 3.1.1) is as follows:

- **Null hypothesis:** the risk of having sequelae 6 months after BJI is **at least** 5% higher when initiating high-dose OT than when initiating IVT ². Formally, $\mathcal{H}_0 : \pi_1 - \pi_0 \geq 5\%$, where π_1 and π_0 are the 6 months risk when initiating high-dose OT and IVT, respectively.

versus

- **Alternative hypothesis:** the risk of having sequelae 6 months after initiating BJI is **at most** 5% larger when initiating high-dose OT than when initiating IVT. Formally, $\mathcal{H}_1 : \pi_1 - \pi_0 < 5\%$.

²As for the definition of the estimand, it is the risk regardless of initiation of any additional interventions during the 6 months follow-up, including switching treatment (from OT to IVT or the other way around), when needed to ensure good clinical care.

4.1 Multiplicity Adjustment

No multiple testing correction will be used, as formal hypothesis testing will be performed only for the primary endpoint/estimand described in Section 3.1.1, for the null hypothesis defined in Section 4.

Reporting for other endpoints/estimands will be limited to point estimates of effects with 95% (two-sided) confidence intervals. The widths of the intervals will not be adjusted for multiplicity and therefore it will not be possible to use them in place of formal hypothesis testing. This is in line with common recommendations [10].

5 Analysis Sets

- The “**Main analysis set**” consists of all randomized participants whose suspicion of infection is not abandoned during the study period and for whom the primary endpoint is not missing. The primary endpoint is missing if the patient did not attend the follow-up after 6 months. More precisely, it is missing if the patient did not attend the “6-month follow-up visit” between 5 and 9 months after randomization.
- The “**Secondary outcomes analysis set**” consists of all randomized participants whose suspicion of infection is not abandoned during the study period. That is, the dataset obtained after adding the patients who did not attend the follow-up after 6-months to the “Main analysis set”.
- The “**All participants analysis set**” consists of all randomized participants.
- The “**Long-term outcomes analysis set**” consists of all randomized participants whose suspicion of infection is not abandoned during the study period and for whom the “12 months follow-up” data are not missing. The “12 months follow-up” is missing if it did not happen between 11 and 14 months after randomization.
- The “**Principal stratum analysis set**” consists of all randomized participants whose suspicion of infection is not abandoned during the study period, for which the primary endpoint is not missing and who did not switch treatment during the initial treatment period following randomization (from OT to IVT or the other way around). That is, the set obtained after excluding from the “Main analysis set” the patients who switched during the initial treatment period.

6 Statistical Analyses

6.1 Primary Endpoint Analysis

6.1.1 Main Analytical Approach

For this analysis we will use the “Main analysis set” detailed in Section 5. We will estimate the primary estimand, that is, the difference in risk $\pi_1 - \pi_0$, as the empirical (i.e. observed) proportion of participants with sequelae after 6 months in the high-dose OT intervention group minus the same proportion in the IVT intervention group. An appropriate one-sided 97.5% confidence interval and a matching p-value for the null hypothesis $\mathcal{H}_0 : \pi_1 - \pi_0 \geq 5\%$ will be computed using an exact

unconditional test. An exact approach will be used instead of alternatives based on (asymptotic) normal approximations, because the expected number of events in each group are very low (say, 0 or 1) and thus usual (asymptotic) approximations do not seem reliable. Specifically, we will use an exact unconditional test using the score statistic ordering, as implemented in the function `uncondExact2x2` of the R package `exact2x2`; see [4] for the mathematical details and Appendix 8.1 for the specific R code that we will use. The score statistic ordering was chosen for its good power properties, as compared to alternatives [4].

If the upper limit of the 97.5% confidence interval of the risk difference $\pi_1 - \pi_0$ does not include the non-inferiority margin 5% or, equivalently, if the matching p-value is less than 2.5%, we will reject the null hypothesis³.

In addition, we will report the estimates of the risk in each group (i.e. the empirical proportions) together with exact binomial two-sided 95% confidence intervals (computed using the `binom.test()` function of R).

Note that the above statistical analyses will ignore that the randomization was stratified by C-reactive protein (< 35 vs ≥ 35). This is usually not recommended, as this usually leads to a decrease in power [5, 8]. However, our context is very specific, as we expect close to zero sequelae in each group (whatever the C-reactive protein level). This has two important consequences. First, the loss of power is expected to be non-existent or negligible. Second, ensuring proper type-I error control using a “covariate-adjusted” alternative approach seems difficult using standard software.

Another important remark also needs to be made, about the rationale for how we deal with the intercurrent event “the suspicion of BJI is abandoned”. Although it is generally agreed that “*the subset of subjects who experience an intercurrent event [here: suspicion of BJI is abandoned] on the test treatment will often be a different subset from those who experience the same intercurrent event on control*”; and therefore that “*Treatment effects defined by comparing outcomes in these subsets confound the effects of the different treatments with the differences in outcomes possibly due to the differing characteristics of the subjects.*” [7] (see also [2] for similar discussions); we do not believe that this is the case in our study (as already mentioned above, in the remark at the end of Section 3.1.1). Therefore, we do not suspect the planned analysis to be biased. Indeed, we think that for each patient for whom the suspicion of BJI is not abandoned, it would not have been abandoned either if the child had been randomized to the other treatment arm. This seems reasonable as the main reason to abandon the suspicion (imaging, blood samples or clinical follow-up reveals another diagnosis) is not expected to be a consequence of the received intervention (OT or IVT). However, in the rare case where the diagnosis remains uncertain, there is a small risk that the treating clinician could abandon the diagnosis of BJI (and thereby ending the antibiotic treatment) in the IVT group more often than in the OT group. This is because IVT is more invasive than OT and therefore the incentive to stop IVT could be stronger than the incentive to stop OT, in case of doubt about the BJI diagnosis. We believe this risk to be negligible and it has been accepted in the overall design of the study, as a minor limitation.

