6.1.2 Sensitivity Analyses

The main analysis is based on the “Main analysis set”, which do not include patients for whom the primary endpoint is missing. This choice is thought to be conservative as it is considered very unlikely that a patient with sequelae at 6-months would not attend the follow-up visit at 6-months.

³Note that the `uncondExact2x2` function guarantees compatible inference via either confidence interval or p-values, so concluding based on the p-value or the confidence interval is fully equivalent here (unlike when using some other software/methods).

This is especially unlikely as telephone interviews focusing on signs of sequelae were planned for all patients not attending the 6 month follow-up.

Nevertheless, we will perform the following sensitivity analysis, for completeness. We will report the results (p-value and upper limit of the 97.5% CI) for all possible combinations of the values of missing outcomes in the OT and IVT groups. An graphical representation similar to the “Enhanced tipping-point display” presented in Liublinska et al. [9, Fig. 2] will be reported, to provide an overview of the results. It will show a heat map of the upper limit of the 97.5% CI (or p-value) for each possible combinations.

As it is considered very unlikely that a patient with sequelae at 6-months would not attend the follow-up visit at 6-months, the results of the sensitivity analysis assuming that none of the patients with missing data had sequelae will be of special interest.

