For the corresponding statistical analysis, we will proceed as for the main analysis detailed in Section 6.1.1, except that the “Principal stratum analysis set” will be used instead of the “Main analysis set”.

The rationale for this statistical analysis is the following. Although it is generally agreed that “*the subset of subjects who experience an intercurrent event [treatment switch in our study] on the test treatment will often be a different subset from those who experience the same intercurrent event on control*”; and therefore that “*Treatment effects defined by comparing outcomes in these subsets confound the effects of the different treatments with the differences in outcomes possibly due to the differing characteristics of the subjects.*” [7], we do not believe that this is the case in our study. Therefore, we do not suspect the planned analysis to be biased. The rationale behind this is the following.

Let Y and S denote the outcome and indicator of treatment switch, respectively, and Y^x and S^x the corresponding counterfactuals for each intervention $x = 0$ (IVT) and 1 (OT); we expect

$$\underbrace{E(Y^1 - Y^0 | S^0 = S^1 = 0)}_{\text{principal stratum estimand}} = \underbrace{E(Y^1 | S^1 = 0) - E(Y^0 | S^0 = 0)}_{\text{estimand of subset analysis}}$$

simply because

$$E(Y^1 | S^0 = S^1 = 0) = E(Y^1 | S^1 = 0) \quad (1)$$

$$\text{and } E(Y^0 | S^0 = S^1 = 0) = E(Y^0 | S^0 = 0) \quad (2)$$

Assumption (1) above is fulfilled if the risk of sequelae is the same among patients randomized to OT who will never switch to IVT, regardless of whether they would have switched to OT if they had been randomized to IVT. Similarly, Assumption (2) is fulfilled if the risk of sequelae is the same among patients randomized to IVT who will never switch to OT, regardless of whether they would have switched to IVT if they had been randomized to OT. We believe these assumptions reasonable as the main reasons for switching (e.g, vomiting that prevents OT) do not seem to share a common cause with the outcome of interest (sequelae); or, at least, not a common cause which has a non-negligible effect on the outcome.

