- Related to the analysis method for outcome S3, in section “*Statistical analyses for the safety outcomes*” of the protocol paper [11], it is written that the number of “*days the child is affected by one or more of these non-serious adverse events*” will also be reported for each arm and compared between arms. Unfortunately, the necessary data to perform this analysis have not been collected. This is because data were collected from the patients or their parents for each adverse event separately. Hence, based on the available data we cannot identify when two adverse events occurred within the same day or at two different days.
- Level of mobility and pain was considered as an “exploratory” outcome in the protocol paper [11], whereas in this SAP we present the corresponding analysis plan in the “*Other analyses*” section (in subsection 6.4.2). This is because no specific statistical inference method is pre-specified to analyze the data about level of mobility and pain (unlike for the other exploratory outcomes).

7 Sample size determination and power calculation

As stated in Nielsen et al. [11], the sample size of 180 children with confirmed BJI (90 in each group) was computed to provide 90% power assuming: a non-inferiority margin of 5%, a risk of sequelae of 1% in both group and 10% dropout rate. The usual asymptotic normal approximations was used, i.e.,

$$\text{Power} \approx \Phi \left(\frac{(0.99 - 0.99) + 0.05}{\sqrt{0.99 \times 0.01/81 + 0.99 \times 0.01/81}} - 1.96 \right) \approx 90\%$$

where $n = 90 \times (1 - 0.1) = 81$ subjects are expected fully observed (with no dropout) in each group and Φ is the cumulative standard normal distribution function, see e.g. Chow et al. [1, Sec. 4.2.2].

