Because the expected number of events in each group are very low (0 or 1) and because we will use an exact test (see Sec 6.1 above), the initial (above) asymptotic power calculation has been suspected to not be sufficiently precise. Hence, an alternative exact power computation was performed and showed that with $n = 81$ subjects in each group, the power is actually approximately 51%, 68% or 82% if we expect 1%, 0.5% or 0.25% risk of sequelae in both group⁵. This suggests that the study is substantially underpowered if there is indeed 1% risk of sequelae in both group, but decently powered if the risk is slightly lower (equal to 0.25%), which is not unrealistic. These additional results complement those presented in the protocol paper [11]. They are the consequence of additional, more recent, thinking.

⁵The computation was performed by computing the likelihood of observing $(x_1, x_0) = (0,0), (0,1), (1,0), (1,1), \dots$ and summing-up the likelihood of each case leading to a significant result, where (x_1, x_0) denote the number of sequelae in the OT and IVT groups.

8 Supporting Documentation

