8.1 R code for the exact unconditional test (Primary Estimand Analysis)

```
library(exact2x2)
uncondExact2x2(x1=x1obs,                                # x1obs is the number of sequelae observed in IVT group
                n1=n1obs,                                # n1obs is the number of patients in IVT group
                x2=x2obs,                                # x2obs is the number of sequelae observed in OT group
                n2=n2obs,                                # n2obs is the number of patients in OT group
                parmtype="difference", # estimand is risk difference
                alternative = ("less"),# one-dided test (non-inferiority)
                method="score",      # score statistic ordering is used
                conf.level = 0.975,   # 97.5% confidence level
                nullparm=0.05,       # non-inferiority margin is 5%
                conf.int=TRUE)      # computation of confidence interval wanted
```

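### At some arm sizes just below plan, the primary exact test fails non-inferiority with zero sequelae in both arms; a small Berger-Boos restriction of the IVT risk prevents this at 75 to 90 children per arm

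*SAP*

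**What the plan says.** Section 3.1.1 sets the margin: "A non inferiority margin of 5% difference in risk was pre-specified". Section 6.1.1 names the test ("we will use an exact unconditional test using the score statistic ordering, as implemented in the function" `uncondExact2x2`) and the decision rule: "if the matching p-value is less than 2.5%, we will reject the null hypothesis". It justifies an exact test by the expectation of 0 or 1 events per arm, and score ordering by its power. Appendix 8.1 gives the call. Its comments include "score statistic ordering is used", but no argument limits the nuisance risk. Footnote 3, attached to Section 6.1.1, says that the "function guarantees compatible inference via either confidence interval or p-values".

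Section 7 starts from 90 per arm with 10% dropout, so that 81 "subjects are expected fully observed (with no dropout) in each group", and reports that "the power is actually approximately 51%, 68% or 82% if we expect 1%, 0.5% or 0.25% risk of sequelae in both group". No other arm sizes are examined. For the principal stratum set, Section 6.1.3 says "we will proceed as for the main analysis detailed in Section 6.1.1".

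**The concern.** An exact unconditional test takes its p-value as the largest tail probability over every possible value of the nuisance parameter, here the IVT risk. Without a restriction, that maximum can fall at an IVT risk far from anything the SAP considers (0.25 to 1%) and far from anything compatible with the data. With about 80 children per arm and a 5-point margin, zero events in both arms only just reaches the 2.5% level, so a small inflation from an irrelevant IVT risk can reverse the decision.

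Zero versus zero is one of the outcomes the SAP expects, and it is the most favourable one for both arms together. The main analysis set depends on attendance at the 6-month visit and on suspicion of infection not being abandoned, so exactly 81/81 is unlikely. If zero versus zero fails at nearby sizes, the primary conclusion depends on an accident of arm size, and Section 7 gives no warning of it.

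**Working it through.** **Inputs.** Margin 5 points (3.1.1); one-sided 2.5% (6.1.1); score ordering (6.1.1, Appendix 8.1); 90 per arm, 10% dropout, 81 evaluable, risks of 1, 0.5 and 0.25% (Section 7). Assumption: the call leaves the IVT risk unrestricted. The test was recoded in Python because R was not available. Pairs are written OT/IVT.

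**Test.** Under the null boundary the OT risk is π₀ + 0.05. Tables are ordered by the score statistic with constrained maximum-likelihood variance, and

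p = max over π₀ in [0, 0.95] of P(Z ≤ z_obs; π₀ + 0.05, π₀).

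Power is the sum of binomial probabilities over tables with p < 0.025.

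**The SAP's figures.**
- Asymptotic: Φ(0.05/√(2 × 0.0099/81) − 1.96) = Φ(3.198 − 1.96) = 89.2%, against about 90% stated.
- Exact at 81/81: 51.5/68.3/81.9%, against 51/68/82% stated. These reproduce.

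**Zero sequelae in both arms, as planned.**

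| OT/IVT | p | IVT risk at the maximum | Non-inferior? |
|---|---|---|---|
| 81/81 | 0.0211 | 38% | yes |
| 78/81 | 0.0226 | 68% | yes |
| 77/81 | 0.0252 | 55% | no |
| 76/81 | 0.0237 | 43% | yes |
| 75/81 | 0.0269 | 59% | no |
| 78/82 | 0.0254 | 55% | no |

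With 81 IVT children, one more sequelae-free OT child (76 to 77) turns success into failure. At 77/81, 0 OT versus 1 IVT event passes (p = 0.0127) while 0 versus 0 does not.

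**Cause.** At an IVT risk of 0 the tail is 0.95^n for n OT children: 0.95^77 = 0.0193, 0.95^78 = 0.0183, 0.95^75 = 0.0213, all below 0.025. The excess arises only at IVT risks of 55 to 59%. With 0 of 81 IVT events, the 99.99% Clopper-Pearson upper limit is 1 − 0.00005^(1/81) = 11.5%.

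**Berger-Boos with gamma = 0.0001.** Maximise only over the 99.99% Clopper-Pearson interval for the IVT risk, then add 0.0001.

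| OT/IVT | p for 0 vs 0: planned → restricted | Power at 1/0.5/0.25%: planned → restricted |
|---|---|---|
| 77/81 | 0.0252 → 0.0215 | 27/23/15% → 53/70/83% |
| 78/82 | 0.0254 → 0.0209 | 28/23/15% → 53/69/83% |
| 75/81 | 0.0269 → 0.0224 | 28/23/15% → 54/70/83% (restricted power run at gamma = 1e-6) |
| 81/81 | 0.0211 → 0.0195 | 51/68/82%, unchanged |

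As planned, power at the three failing pairs drops as the true risk drops, because zero versus zero becomes the dominant outcome and does not count. The upper limits for 0 versus 0 move from about 5.0% to 4.8% (77/81) and from about 5.1% to 4.8% (78/82). The maximum type I error of the restricted test at 77/81, computed for gamma = 1e-6, is 0.0248.

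**How often.** Failing pairs are 2 of 81 with both arms at 77 to 85, and 17 of 256 with both arms at 75 to 90. Both counts become 0 with the restriction.

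| Scenario | Chance that arm sizes make 0 vs 0 fail | Power averaged over sizes, 1/0.5/0.25% |
|---|---|---|
| 10% dropout per child from 90/90 (SAP) | 5.0% → 0.4% | 50/66/79% → 51/68/82% |
| 162 children split at random (assumed) | 19% → 7% | 47/60/69% → 51/66/78% |
| 15% dropout (assumed) | 38% → 14% | 43/51/57% → 49/63/73% |

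**Principal stratum set.** The SAP gives no switching rates. Starting from 81/81, assumed switching of 5% in OT with 0, 2 or 5% in IVT gives a 42, 20 or 22% chance of a 0 versus 0 failure. With the restriction this becomes 0.7, 3.5 or 3.8%. Switching of 3% in OT and none in IVT gives 16%, which becomes 0%.

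**The case against.** Nothing in the SAP is false here. The test holds its level, the stated power is right, and maximising over the nuisance risk is how the unrestricted test guarantees that level. Choosing between two valid exact tests can be called optimisation. Under the SAP's own dropout rate the chance of a bad pair is 5.0% and averaged power rises by only 1 to 3 points. Of the 17 failing pairs at 75 to 90, 14 have only 75 or 76 OT children and none has more than 78. The larger figures rest on a random split, 15% dropout or switching rates the SAP does not give. Section 6.1.3 is supplementary, and formal testing is confined to the primary estimand. The tipping-point display in 6.1.2 would show results for larger arms. A late change that makes one particular result pass may look data-driven in an open-label trial.

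Much of this stands, and it limits the weight of the point. It does not remove it. When a bad pair occurs, the most favourable result possible is lost, in a trial that Section 7 already calls substantially underpowered at 1% risk. The tipping-point display does not alter the primary decision. The fear of a data-driven change is a reason to fix the rule before unblinding.

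Two limits remain. The unrestricted default is inferred from the SAP's text and code, and the 81/81 power cannot confirm it because both versions give the same value there. The restriction also does not rescue every small arm: 74/78 still fails (p = 0.0254 at gamma = 1e-6), and nothing helps with 71 or fewer OT children, since 0.95^71 = 0.026.

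**Conclusion.** The point holds and should be acted on, as an avoidable weakness in the specification and not as an error of validity. If the IVT risk is unrestricted, zero versus zero fails at 77/81, 78/82, 75/81 and other nearby pairs, in no orderly pattern. Power there is roughly 15 to 28%, against 53 to 83% with the restriction. At 81/81, at equal arms of 75 or more, and with 80 or more OT children, zero versus zero passes and this problem does not arise. The probability of meeting it is about 5% under the SAP's assumptions and rises steeply if dropout is somewhat higher. The principal stratum analysis is more exposed than the main one, because removing switchers makes the arms smaller and often unequal; how much more depends on switching rates that had to be assumed.

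**What to change.** Before unblinding:

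- In Section 6.1.1 and Appendix 8.1, keep score ordering and the 2.5% level. Add a Berger-Boos restriction with gamma = 0.0001, using the 99.99% Clopper-Pearson interval for the IVT risk from the IVT arm alone, with 0.0001 added to the p-value and the same rule for the upper limit. State gamma and how the set is formed.
- Keep gamma small. Of the 256 pairs at 75 to 90, none fails zero versus zero for gamma from 1e-6 to 1e-3, but 50 fail at 0.005, against 17 as planned.
- Confirm in the final code that p-value and upper limit still agree, as footnote 3 requires. They agreed in every case tried: outcomes 0/0, 0/1, 1/1 and 1/2 at 81/81, 77/81 and 78/82.
- Apply the same rule in Section 6.1.3.
- In Section 7, report exact power and the zero-versus-zero decision over equal and unequal arm sizes, for example 72 to 90.

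The cost is a short change to the text and code, the 0.0001 penalty, and one more prespecified choice to defend. The test stays exact, and there is no gain at 81/81.
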